Most contraceptive methods are highly (>90%) *efficacious* but are prone to user error, compromising *effectiveness* in real-world settings. 48% percent of women with unintended pregnancies report using contraception during the month of conception.¹² Most young women rely on short-acting or coitally-dependent methods like oral contraceptive pills (OCs) or condoms.¹³ Half of young women report imperfect OC use, with about 25% missing ≥2 pills in a cycle.¹⁴ However, long-acting reversible contraceptive (LARC) methods like the intrauterine device (IUD) require few use behaviors while providing *effective* (>99%) and *long-lasting* (3-10 years) protection against pregnancy.¹⁵ Yet, <7% of women using contraception in the United States (US) use LARC, with rates lowest among those at highest risk of unintended pregnancy.¹³

Need for Novel Dual Protection Interventions

The significant reproductive health disparities of young AA women demonstrate the need for novel interventions that promote dual protection and account for their unique reproductive health challenges and life contexts. The few clinic-based interventions designed to increase dual protection have largely been unsustained or have failed to result in statistically significant effects.¹⁶⁻¹⁸ Young women receiving a computer-based, tailored intervention reported increased dual method use, but no change in STIs and unintended pregnancies compared to controls.¹⁹ Reanalysis of the data showed 32% initiated dual method use, but only 9% sustained use.²⁰ A video counseling intervention for AA and Latino female adolescents increased condom use at three months post-intervention, but not at 12-month follow-up.²¹ However, we should remain hopeful about reducing such disparities. In a large-scale study, when barriers to all contraceptive methods were lowered and LARC was presented as the optimal method, rates of LARC uptake surpassed 65% and pregnancy and abortion rates declined.^{15,22} While efforts have traditionally focused on improving condom use, there is evidence that youth rely on many dual protection strategies.²³ Thus, interventions must address multiple types of “dual protection”.²⁴

Need for Scalable, Brief Interventions

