key change process is enhancing awareness. Video vignettes that present common behavioral, normative, and control beliefs, constructs from the **Theory of Planned Behavior** (TPB), can address acquisition of a new behavior. For those who are in or move to the *Contemplation* stage, the key necessary change process is to “tip” decisional balance. **Motivational interviewing (MI)** teaches that an efficient and effective strategy for helping to “tip” the decisional balance is to explore and resolve ambivalence, something not typically used in less effective counseling processes, which tend to impose a solution. We will employ elements of motivational interviewing, which we term **MI-informed counseling**, including: collaborating as partners, empathic understanding, autonomy support, and self-efficacy support. Consistent with our conceptual model, a **Risk Reduction** framework for dual protection is incorporated. LARC with condoms is the optimal option, but it is not the only option. Risk reduction frames prevention behaviors along a continuum rather than in binary terms, recognizing opportunities for incremental behavior change, especially when behaviors are suboptimal.⁵⁰ Thus, STI/HIV messages will also center on behaviors including condom use, partner negotiation, limiting the number of sexual partners, STI testing after unprotected sex, avoiding alcohol and drug use, and use of expedited partner therapy. These behaviors reduce risk even among condom users.²⁴ Finally, both women and men will be portrayed in videos to ensure that the educational messages are patient-centered, salient, authentic, and relevant. **Human-Centered Design (HCD)**, a design approach recently applied to health care, ensuring that interventions meet the needs of the community of users, **will be used to create a usable, sustainable intervention.**⁵¹ In HCD, the designer and end-user collaborate to create solutions in an iterative process of rapid prototyping with key stakeholder participation. Resulting interventions are based on available technology, address true barriers, and are matched to a realistic understanding of behaviors, skills, and informational needs. We will use HCD best practices such as iterative low-fidelity prototyping and multiple course corrections before a final solution is achieved.

2. Hypotheses

We hypothesize that post-intervention, patients using *miPlan* will report:

H¹ a significant increase in contraceptive continuation and condom use

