recruitment and minimize clinic interruptions. Training will include how to use the *miPlan* app, identify and address ambivalence, and support strategies for managing anticipated barriers. [name], an experienced MI counselor, will oversee training, providing didactic presentations on core concepts of the TTM, including stages and process of change and decisional balance. [name] will oversee training related to condoms and contraceptive methods.

Aim 2: Conduct a pre/post feasibility, acceptability, and effectiveness assessment of *miPlan* to examine improvement in dual method use, enhancement of contraceptive adherence and continuation, increase of condom use, and decrease of STI/HIV infection.

Recruitment and Enrollment. All research activities will take place at the DCAM at the University of Chicago and select Planned Parenthood-IL clinics(Austin, Englewood, and/or Roseland).. We will pre-test the app and study procedures with 5 participants (compensation=\$50), following the protocol planned for the pilot study. At their clinical visit, participants who meet the inclusion criteria (n=100) will be referred by clinic staff to a trained on-site RA, who will explain the study and complete the informed consent process. Inclusion criteria are: (1) Being AA female and sexually active with a male partner(s) within the past 6 months; (2) Age 15-25 years; (3) Initiating contraception; (4) Not currently pregnant or intending pregnancy within the next 6 months; (5) English speaking; and (6) Not currently using LARC. As Illinois law ensures the rights of minors to receive confidential reproductive health care without parental consent, we will seek a waiver of parental consent for participation of those 15-17 years old.

Pre-Intervention Baseline (T1) Procedures. Participants will complete a 10-15 minute questionnaire on the *miPlan* app (See appendices). The RA will provide a brief orientation to the *miPlan* app. After viewing *miPlan*, participants will be guided through a MI informed conversation using a worksheet to document the discussion on contraceptives knowledge and usage. The completed worksheet will be given to the participant and a copy will be kept for the participant's records. (10 min). The participant will receive educational materials and a strategies worksheet to discuss with their clinician. The participant will also be given an STI test. Participants will be compensated \$30.

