Post-Intervention (T2) Procedures. At 6-weeks post-enrollment, participants will complete a 15-25 minute phone survey to gauge dual method use, contraceptive adherence/uptake, frequency of unprotected penile-vaginal/anal intercourse (PVI/PAI), and risk reduction behaviors. Participants will be compensated \$20.

Follow-Up (T3) Procedures. At 3 months post-enrollment, participants will complete a 15-25 minute in-clinic survey to gauge maintenance of dual protection behaviors, contraceptive adherence/uptake, frequency of penile vaginal intercourse/penile anal intercourse, risk reduction behaviors, decisional balance/self-efficacy, and an STI test. Participants will receive \$40. We will also conduct a 3-month retrospective chart review to capture interceding visits (e.g., initial contraceptive method selection, method switching, etc.) and diagnoses (e.g., pregnancy, STI/HIV). Participants unable to come in to clinic for their followup visit or who do not wish to come to clinic will be offered an at-home STI screening kit, to be mailed to the address they

provide. Participants who wish to be sent a kit will be mailed a endo-cervical screening kit, via USPS priority mail, with pre-paid postage and instructions for using the administering the self swab to themselves and packaging and mailing the completed kit back to Ci3. No identifying information will be included in the mailing, and all costs with mailing and processing will be paid by Ci3. All participants will be offered the at-home screening option upon reaching their three month follow-up event, and can complete the survey over the phone or online.

4. Duration

We are requesting IRB approval for a portion of Aim 1 to develop and pilot test the miPlan app and Aim 2 which cover months 3-21 of the overall study.

5. Location

The study will be conducted at the Duchossois Center for Advanced Medicine (DCAM) at the University of Chicago . The DCAM is home to adult primary and specialty clinics, pediatric specialty clinics, and outpatient diagnostic and treatment facilities of the University of Chicago Medicine. The will also be additional sites at Planned Parenthood-IL clinics, Austin, Englewood, and/or Roseland.

6. Special Precautions

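### H1 predicts a pre/post increase in contraceptive continuation, but women enrol while initiating contraception and there is no control, so continuation of the method being started has no baseline value

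*Combined protocol and SAP*

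**What the plan says.** H1 (Section 2) expects women using miPlan to report "a significant increase in contraceptive continuation and condom use" after the intervention. Aim 2 (Section 3) is a pre/post assessment meant "to examine improvement in dual method use, enhancement of contraceptive adherence and continuation", among other outcomes. Section 7 confirms that there is no control arm.

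The inclusion list under Recruitment and Enrollment contains "3) Initiating contraception; (4) Not currently pregnant or intending pregnancy within the next 6 months; (5) English speaking; and (6) Not currently using LARC". At T1 each woman completes the questionnaire, uses the app and has the counselling conversation. Then, "The participant will receive educational materials and a strategies worksheet to discuss with their clinician". The method may therefore be settled only after the baseline questionnaire. The 3-month chart review is planned "to capture interceding visits (e.g., initial contraceptive method selection, method switching, etc", and the 3-month survey (T3) is "to gauge maintenance of dual protection behaviors, contraceptive adherence/uptake".

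Section 9 gives implant with condoms and IUD with condoms as example outcome categories for a multinomial model. It does not say whether T1 observations enter that model. In the supplied text, continuation is named only in H1 and in the Aim 2 statement. It is not defined, and no comparison rate is given.

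**The concern.** A pre/post increase needs the same quantity measured before and after. Continuation describes what happens after a start, and here the start coincides with entry to the study or follows it. Without a control group or a stated external rate, nothing remains against which continuation could be said to have increased. An analyst following the plan would have to invent a T1 value, and the result would depend on that choice.

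The definition also matters in its own right. Section 1 says that "LARC with condoms is the optimal option, but it is not the only option", and the chart review expects method switching. If continuation means staying on the same method, a woman who moves to LARC counts as having stopped, although the intervention favours that move.

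The LARC-plus-condom categories raise a smaller version of the same problem. Eligibility fixes their T1 count at zero, so a change in them can only point one way.

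**Working it through.** The plan has no calculation to reproduce. It gives 100 women but no significance level, event rate or dropout rate. The argument is structural, and the figures below only illustrate scale. All follow-up counts are assumptions.

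**Continuation.** Inputs are criterion 3 (all women initiating), Section 7 (no control) and H1 (an increase).

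- Let S be the women who start a first method, and C(t) those still using it at time t. C(t) is a subset of S.
- At T1 the method is only being started, so C(T1) has no observed value.
- If T1 were nonetheless set to 100%, the change would be |C(t)|/|S| − 1, which is at most zero. An increase cannot occur.
- If T1 instead held use of an earlier or different method, follow-up minus T1 could be computed. It would be a change in contraceptive use, or uptake.

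**What the follow-up data can give.** The Wilson 95% interval is [p + z²/2n ± z√(p(1−p)/n + z²/4n²)] / (1 + z²/n), with z = 1.96. For n = 100, z²/n = 0.0384 and z²/2n = 0.0192.

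- First method still in use, assumed 70/100: centre (0.70 + 0.0192)/1.0384 = 0.693, half-width 0.088, interval 60.4% to 78.1%. With an assumed 80 women retained, 56/80 gives 59.2% to 78.9%.
- If 15 more women had switched, any-method use would be 70 + 15 = 85/100, interval 76.7% to 90.7%. The two definitions then differ by the 15 points of switching. This assumes that all 100 started a method.

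**LARC plus condoms.** Criterion 6 makes the T1 count 0, so the change is X(t)/n − 0, which is never negative.

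- Uptake of an assumed 6/100: centre (0.06 + 0.0192)/1.0384 = 0.076, half-width 0.048, interval 2.8% to 12.5%. For 6/80 it is 3.5% to 15.4%.
- If someone tested this against the fixed zero at an assumed two-sided 0.05, exact McNemar would give 2 × 0.5⁶ = 0.031 for six users and 2 × 0.5⁵ = 0.0625 for five. Fisher's test on 100 women gives 0.029 and 0.059. The dividing line is six women.
- The probability of six or more users among 100 is 1.5%, 38% or 94% if true uptake is 2%, 5% or 10%.
- If T1 rows entered the multinomial model with time as a predictor, these categories would have no T1 events. Their time coefficients would not be estimable by ordinary maximum likelihood.

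**The case against.** The strongest reply is that a baseline may exist. The T1 questionnaire is in appendices that were not supplied, and initiating is undefined. Criterion 6 would be nearly redundant if criterion 3 admitted only non-users, so current users of other methods may be eligible. Section 1 also notes that "Most young women rely on short-acting or coitally-dependent methods like oral contraceptive pills (OCs) or condoms". This stands in part: a pre/post change in use of any method may be computable for some women. That does not rescue H1, because prior use of one method is not a T1 value for continuing another.

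On LARC plus condoms, H1 does not name the outcome, Section 9 lists it only as an example category without a stated T1 contrast, and the T2 and T3 procedures already refer to uptake. Follow-up minus zero is also a valid number. All of this stands, and it makes the point secondary.

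A reader might also infer more than the documents support:

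- That all of H1 fails. Its condom-use half can have a T1 value.
- That any dual method use is zero at T1. Criterion 6 fixes only the LARC combinations.
- That the analysis would report a spurious fall in continuation. No section codes T1 as 100%; that coding is used here only to show that the predicted direction is unattainable.
- That a significant LARC result is assured. The probabilities above show that it is not.

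**Conclusion.** The concern holds for the continuation half of H1. As worded, the predicted increase cannot be shown, because the method being started has no T1 value and the study has no comparator. This follows from the eligibility criteria and the design, and does not depend on the assumed counts. It would be weakened only if the unsupplied appendices defined continuation as something other than persistence with the method started, in which case the term should be changed.

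The zero baseline for LARC plus condoms is certain from criterion 6 but secondary. The multinomial difficulty arises only if T1 rows are modelled.

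This should be fixed before analysis, but it does not undermine the study. With about 100 women, the planned data would estimate continuation to within roughly 9 points either way at an assumed 70%.

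**What to change.** 1. Reword H1, the Aim 2 statement and Section 9 so that continuation is a follow-up outcome at T2 (6 weeks) and T3 (3 months) after enrolment, given as a proportion with a 95% confidence interval and no pre/post test. Report two versions:
   - still using the first method started, among women who started one;
   - using any contraceptive method, among all enrolled women with follow-up.

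   State separately how many women never started a method. The second version keeps a switch, including to LARC, from counting as stopping contraception.
2. Report LARC-plus-condom use as uptake at T2 and T3 with a 95% confidence interval. Fit any multinomial model containing these categories to follow-up observations only.
3. Keep pre/post analyses, using paired methods, for outcomes that have a T1 value, such as condom use and any dual method use. State whether initiating includes women switching or restarting.

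The cost is protocol and analysis wording, plus items for prior method and method start date if the existing forms lack them. No new visits are needed. The real loss is the significance claim for continuation and for LARC-plus-condom use. Recovering a comparative claim would need a concurrent control or a justified external rate, and the documents provide neither.

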Brief, inexpensive, practical, and theoretically-based interventions may hold promise for reaching large numbers of people. A growing body of research²⁵⁻²⁷ suggests that brief interventions relying on more than just information can be successful.²⁸⁻³³ Interventions with strong behavioral models, focused information, and opportunity to address potential barriers to change tend to report stronger effects.^{28,29}

Importance of E-health, Health Information Technology and Counseling Aids

Interactive multimedia programs present a novel platform for delivering interventions.³⁴ Digital media provides an opportunity to scale interventions and reach the broad population of youth necessary to reduce STI rates. Tailored, theory-based digital interventions have been effective in smoking cessation,³⁵ reducing repeat births among low-income AA adolescent mothers,³² promoting adherence to antiretroviral medications,³⁶ and increasing awareness of diabetes complications.³⁷ Users of a touchscreen computer intervention were significantly more likely to choose highly effective contraception.³⁸ Multiple programs have successfully taken advantage of clinic wait times^{37,39-41} without obstructing patient flow. HIV-positive users of a counseling tablet found it reduced social bias, promoted honesty in discussing sensitive topics, and promoted privacy.⁴²

Key Theories and Approaches Informing this Intervention

The **Transtheoretical Model** (TTM) and its Stages of Change paradigm posits that in changing behaviors, individuals progress through sequential stages of *Pre-contemplation*, *Contemplation*, *Preparation*, *Action* and *Maintenance*. Transition between steps requires a core set of change processes.⁴⁹ Women seeking contraception are most likely in *Pre-contemplation* or *Contemplation* stages for adopting dual method use including LARC. For *Pre-contemplation*, the

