The primary risks are loss of confidentiality and potential discomfort associated with answering sensitive questions about STIs, HIV, and sexual risk behaviors. All participants will be assigned a unique study identifier. Once all data has been collected, identifying subject information (including name) will be stripped from the database and from transcripts of focus group and in-depth interviews. Informed consents with the subjects' names will be stored at the University of Chicago and only accessible to designated research staff. Consent forms will be stored in a locked filing cabinet in a locked office at the University of Chicago. Reports, manuscripts, and presentations will never include identifying information. With respect to potential discomfort associated with answering sensitive questions, subjects will be informed that they can skip any question they do not want to answer without penalty and that they can opt out of the study at any time without penalty. Participants are informed of these protections in the consent forms and all relevant study documents.

7. Experimental Controls

Not applicable. This is a pre- and post- intervention

8. Type and number of subjects

During Aim 1, we will recruit users in the clinic waiting room (n=7) to use the app prototype in 20 minute sessions, filming their hands as they use it, taking notes as they navigate aloud, and making changes in response to their feedback.

During Aim 2, we will pre-test the app and all study procedures with 5 women. In the pre- and post-intervention, we will recruit 100 young women (ages 15-25) from the waiting room of a gynecology clinic at the University of Chicago and select Planned Parenthood-IL clinics.

9. Statistical Analysis

Feasibility & Acceptability: Descriptive statistics will be used to analyze the proportions and central tendency for satisfaction, helpfulness, appropriateness, and usefulness of *miPlan*.

Effectiveness: Outcome variables will be measured in the following ways: Chi-square or Fisher's Exact Test (categorical variables); *t* test and Mann-Whitney U test (continuous variables); and multinomial logistic and linear regression models. Multinomial logistic regression models will be used based on multiple categories for dual method (e.g., use of oral contraceptive with condoms; implant with condoms; or IUD with condoms). Linear regression and probability models will be used with the categorical dual method collapsed (e.g. any dual method).

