Participants in the iterative design process, pre-test and pilot will be recruited by research staff from the clinic waiting room at University of Chicago and select Planned Parenthood-IL clinics. A qualified member of the research staff will conduct eligibility screening to ensure participant eligibility. This member of the research staff will also work with clinicians in order to identify potentially eligible patients who have scheduled appointments during the recruitment phase of the study. These patients will be telephoned in advance and informed that they may be able to participate in the study during their medical visit. Eligible participants will be consented and enrolled. Research activities will take place at the University of Chicago and select Planned Parenthood-IL clinics. The informed consent process will inform the participant that participation is completely voluntary and that a decision not to participate will not affect her care at the University of Chicago or Planned Parenthood.

17. Primary Physician Notification

Not Applicable

18. Interdepartmental Coordination

Not Applicable

19. Pregnancy Test

Not Applicable

20. Rationale for Exclusion

Because the present study is focused on preventing STIs and pregnancy among young African American women, we will exclude non-African American subjects. We also will exclude any prospective participant with a cognitive deficit that precludes providing informed assent/consent.

21. Medication Infusion

Not Applicable

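### Eligibility ignores the method a woman already intends to start, so choices made before the app count as post-intervention uptake and, for condom users, as new dual-method use

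*Combined protocol and SAP*

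**What the plan says.** Section 3, Aim 2, Recruitment and Enrollment, sets two criteria on contraception: "3) Initiating contraception" and "6) Not currently using LARC". The exclusions in Section 20 concern race and capacity to consent. None of these refers to a method already chosen.

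Section 1 (Key Theories) places most women seeking contraception in the two earliest "stages for adopting dual method use including LARC". This is stated as a likelihood and is not an entry condition.

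The Aim 2 purpose is "to examine improvement in dual method use, enhancement of contraceptive adherence and continuation, increase of condom use", plus a decrease in STI/HIV. Uptake is gauged in the T2 and T3 surveys, and the three-month chart review captures "initial contraceptive method selection, method switching, etc".

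Section 7 on experimental controls reads "Not applicable. This is a pre- and post- intervention". Section 8 adds that "we will recruit 100 young women (ages 15-25) from the waiting room". Section 9 models dual method use in categories that include implant with condoms and IUD with condoms, and also as any dual method. It screens covariates at p < .20 and does not name intended method as a covariate, a stratum or part of an outcome definition.

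**The concern.** A woman who comes to the clinic to have an implant placed is starting contraception and is not yet a LARC user, so she is eligible. She completes T1, sees the app, has the counselling and receives the implant she came for. The chart review and follow-up surveys then record a method started after miPlan. If she was already using condoms, she moves from no LARC-plus-condom use at T1 to LARC-plus-condom use at follow-up, and none of that movement need be due to the intervention.

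With no control group, the pre/post change is the only evidence of effectiveness, and the stated analysis cannot separate this movement from change that miPlan produced. Reported uptake, and to a lesser degree reported dual-method improvement, would be too high by an unknown amount. Intention before exposure cannot be reliably recovered afterwards, so it has to be recorded at T1.

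**Working it through.** The plan states no power, effect size, alpha or expected uptake for its 100 women, so there is no figure to reproduce. What follows is illustration, using two-sided 0.05 as an assumed level.

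**Inputs from the protocol**
- N = 100 (Section 8).
- LARC use at T1 = 0, because criterion 6 excludes current users.
- No comparison group (Section 7).

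**Assumed inputs (the documents give none of these)**
- Share arriving already intending LARC: 10% to 30%.
- Share of those who receive it: 80%.
- Share of those who already use condoms: 30% to 50%.

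**Step 1: how few LARC starts look significant.** With T1 fixed at 0, every change is in one direction, so the exact paired p for k starts is 2 × 0.5^k.
- k = 5: 2 × 0.5^5 = 0.063
- k = 6: 2 × 0.5^6 = 0.031
- k = 8: 2 × 0.5^8 = 0.008

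Section 9 names Fisher's exact test, an unpaired test; for 0/100 against 6/100 it gives p = 0.029. Either way the threshold is six women.

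**Step 2: pre-decided LARC starts.**
- Low: 100 × 0.10 × 0.80 = 8
- High: 100 × 0.30 × 0.80 = 24

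**Step 3: chance of six or more starts with no app effect**, where s is the share who arrive decided on LARC and receive it (binomial, N = 100).

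| s | P(at least 6) |
|---|---|
| 2% | 1.6% |
| 5% | 38% |
| 7% | 71% |
| 10% | 94% |

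With 80 women retained (assumed), the last three become 21%, 49% and 82%.

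**Step 4: carry through to dual use**, which is what Aim 2 names and Section 9 models. A pre-decided LARC start enters a dual category only if condoms are also used.

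| Pre-decided LARC starts | 30% use condoms | 50% use condoms |
|---|---|---|
| 8 | 8 × 0.30 = 2.4 | 8 × 0.50 = 4 |
| 24 | 24 × 0.30 = 7.2 | 24 × 0.50 = 12 |

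So about 2 to 12 new LARC-plus-condom users could appear with no miPlan effect. At the low end (2.4%), the chance of six or more among 100 is about 3%. At 12% it is about 98%. The effect on dual use therefore runs from negligible to decisive, depending on two shares that the documents do not give.

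**The case against.** Several stronger readings are tempting, and the documents do not support them.

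- **A reader might infer that miPlan has nothing left to change in a pre-decided woman.** Section 1 makes dual protection the target and lists condom use, partner negotiation and STI testing among the behaviours addressed. Section 3 (Develop the MiPlan app) designs for users at different stages of change. A woman set on an implant is still in the target population for the condom and STI half.
- **A reader might take the LARC p-values as the trial's false-positive risk.** LARC uptake alone is in neither H1 to H5 nor the Aim 2 statement. An implant without condoms adds nothing to the dual categories. The p-values show only how little is needed when T1 is fixed at zero.
- **A reader might infer that Section 16 selects for pre-decided women,** since staff "identify potentially eligible patients who have scheduled appointments during the recruitment phase of the study". The visit type is not specified, and women also come from the waiting room and by staff referral. No such tilt is shown.
- **A reader might infer that intention is not collected.** The T1 questionnaire is in appendices not available here and may already ask. Only the lack of any analytic use is established.
- **A reader might infer that intention data would isolate the miPlan effect.** Every participant is at a visit to start contraception and will see a clinician, so undecided women can also take up a method without miPlan.

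It is also fair that the assumed 10% to 30% is unanchored. Section 1 says fewer than 7% of US contraceptive users use LARC. That is prevalence, not intention, but 7% × 80% gives 5.6 expected starts, just under six, with about a 49% chance of reaching six. Section 1 also cites uptake above 65% once barriers were lowered, so the documents do not settle the share.

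These points limit the size and reach of the concern. They leave its core standing: the plan admits pre-decided women, measures uptake, has no control, and does not use prior intention.

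**Conclusion.** The concern holds as a gap in how uptake is defined and reported. Under the plan as written, a method chosen before exposure counts as post-intervention uptake and, with condom use, as dual-method improvement. H1 to H5 do not name method uptake and are less directly affected.

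The size is unknown. Six LARC starts from zero would reach p = 0.031. Under the assumptions shown, about 2 to 12 new dual users could arise with no miPlan effect. These figures rest on assumed shares for prior LARC intention, receipt and condom use, and on T1 LARC being zero by criterion 6.

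This is a cheap improvement worth making. It does not show that the pilot's results would be invalid, and it does not call for excluding pre-decided women.

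**What to change.** 1. **T1 questionnaire.** Before any miPlan content or counselling is seen, record the method the woman intends to start and her intention or stage of change for condom use. The questionnaire is delivered on the app itself, so the protocol should state that these items come ahead of the educational content. If the T1 appendix already has such items, use them.
2. **Section 9, definition.** Define the method-uptake result as the shift from pre-app intended method to the initial method in the chart.
3. **Section 9, reporting.** Report LARC and dual-method uptake separately for women who did and did not already intend that method, with those who did not as the main uptake result.
4. **Analysis set.** Leave eligibility unchanged and keep all 100 women in the condom, dual-use, adherence and STI analyses. Pre-decided women can still change on all of these, and dropping them would discard Aim 2 outcomes.
5. **Limitation.** State that this removes only the pre-decided part of the bias, and that uptake still cannot be attributed to miPlan without a comparison group.

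The cost is two or three questionnaire items at most and a few sentences in Section 9. The main uptake result will have a denominator below 100, so it will be less precise, and the headline uptake will probably be lower.
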